AdhereTech has created patented smart pill bottles that improve medication adherence. These bottles automatically measure the number of pills in the bottle in real-time, and wirelessly transmit this HIPAA-compliant data to a central server. If a patient hasn't taken his/her medication, the technology is able to remind them via phone call or text message. The AdhereTech bottle also has on-bottle lights and chimes that are automatically triggered to remind patients to stay adherent. When patients receive reminders the via a phone call, patients can leave feedback and information as to the main reason why they didn't take a dose (e.g., side effects, lack of information, lack of symptoms, or any other issues.) Patients use the AdhereTech bottles in the same way they use normal pill bottles. The bottles have a cell phone chip build inside, so they can work anywhere as they collect and send adherence data. The bottles never need to be charged or kept in a particular location, so patients can travel with the bottles. Thus, little, if any behavior change is needed to effectively use this adherence-promoting device.

[figure not shown]
Tenofovir disoproxil fumarate (TDF, trade name: Viread) is a nucleoside analogue that is a preferred first-line drug in current HIV treatment guidelines (DHHS). TDF is used commonly as part of 3 available one-pill, once-daily combination HIV drug regimens: TDF + emtricitabine + efavirenz (Atripla), TDF + emtricitabine + rilpivirine (Complera), and TDF + emtricitabine + elvitegravir + cobicistat (Stribild), and is used commonly in other HIV regimens. TDF is phosphorylated intracellularly to tenofovir diphosphate (TFV-DP), a compound with a long half-life of 17 days in cells; the measurement of TFV-DP drug levels in dried blood spots recently was shown to estimate average drug exposure over 12 weeks (Castillo-Mancilla). This longer term measure of adherence can be compared with plasma tenofovir levels that estimate short-term adherence over 1-3 days.

We propose to conduct a randomized, pilot study of the novel adherence intervention, AdhereTech bottles with reminders, in HIV-infected patients with documented suboptimal adherence to their TDF-containing antiretroviral regimen.

STUDY SCHEMA:

See below

HABIT

Abbreviations: TDF – tenofovir disproxil fumarate, TFV-DP - tenofovir diphosphate (TFV-DP), TFV – tenofovir 4

STUDY OBJECTIVES AND ENDPOINTS:

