- Planned HIV treatment interruption in the last 52 weeks or anticipated interruption in the next 12 weeks
- Any condition that would interfere with study participation in the opinion of the investigator
- Individuals considered by the study investigators to be unlikely to participate in intensive follow-up and/or unwilling to provide blood samples.
- Individuals with significant cognitive or psychiatric illness, which limits their capacity to fully understand or provide written informed consent for the study.

Special groups:

This study may enroll special groups of subjects, including those with mental illness. People infected with HIV sometimes have psychiatric co-morbidities including depression, anxiety, schizophrenia, and/or substance abuse. The investigators in this study are experienced at treating patients with HIV and psychiatric co-morbidities, and only subjects determined by the investigators to be mentally stable enough to fully understand the study and to provide written informed consent will be enrolled. The investigators may withdraw subjects if it is in the best interest of the subject.

Study Design:

Study Overview:

This is a randomized, open-label, 12-week pilot study involving 70 HIV-infected subjects taking a tenofovir-containing antiretroviral regimen with documented suboptimal adherence over the prior 52 weeks. Subjects will be randomly assigned to study groups in a 1:1 ratio with the use of a computer-generated randomization table. 35 subjects will receive usual care with routine adherence counseling and 35 subjects will receive routine adherence counseling plus a novel adherence intervention – the AdhereTech bottle with phone call or text message reminders.

Study Visits:

At screening, all patients will sign an informed consent form (Appendix A) and undergo a baseline history and physical exam. The history will elicit demographic information (gender, age, race, ethnicity), past medical history/current co-morbidities, current HIV medical regimen, and history of psychiatric disease and substance use. Upon enrollment, all patients will receive standard counseling regarding the importance of HIV medication adherence. Each subject assigned to the novel adherence intervention group will be supplied one AdhereTech bottle and the research team will transfer all of their tenofovir-containing medication to the bottle (either a single tablet combination anti-retroviral medication or the tenofovir component of a multi-pill antiretroviral

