The ongoing choice of a patient's HIV antiretroviral regimen will be at the discretion of his/her primary provider, who will not be involved directly in this study. In all circumstances, the health and welfare of the patient will take precedence over study participation and as such, they will be provided with sufficient information about alternative treatments that may be offered outside of the study. If a patient's treating provider decides that s/he should no longer be on a tenofovir-based regimen during the course of the study, the reason for this change will be recorded, the adherence intervention will be discontinued, and the patient will remain in the study for the purpose of an intention-to-treat analysis.

Early Withdrawal:

Any patient who wishes to withdraw from the study is able to do so at any stage. These patients will be encouraged to attend a follow-up visit prior to withdrawal in order to discuss reasons for withdrawal, as well as any safety issues that may be relevant. At this visit a follow-up questionnaire and blood samples will be collected (as per a normal follow-up visit).

Discontinuing a Patient:

Patients will be discontinued from the study if, at any time, they are considered by the study investigators to be unlikely to participate in the necessary follow-up (i.e. due to an inpatient hospital admission, change of residence, incarceration, or a severe medical/psychiatric illness that precludes the patient's ability to make clinic visits or comprehend study procedures) and/or if the patient becomes unwilling to provider blood samples while on the study. In such cases, the adherence intervention will be discontinued and the patient will remain in the study for the purpose of an intention-to-treat analysis.

Duration/Length of follow-up:

Each patient will be followed for a total of 12 weeks after enrollment.

STATISTICAL CONSIDERATIONS AND DATA ANALYSIS PLAN:

Sample Size Estimate:

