In this pilot study, the sample size calculation is based on the null hypothesis of no difference in tenofovir-diphosphate (TFV-DP) concentrations (by dried blood spots) at baseline versus a demonstrable difference at week 12. From a simulation study (Castillo), we expect to see the same mean concentration (standard deviation) at both groups at baseline: 900 (404) fmol/punch. At 12 weeks, we expect to see a mean concentration (standard deviation) of 1332 (597) fmol/punch in arm A (adherence intervention) vs. 900 (404) fmol/punch in arm B (control). Assuming normal distribution of TFV-DP concentrations, type 1 error = 0.05, power = 80%, a sample size of 32 will be recruited per arm (64 total) based on a two-sided, two-sample t-test with equal variance. Since the data may have missing data at the last visit, we will add ~10% more participants. Therefore, the final sample size of 35 per arm (70 total) will be enrolled.

We intend to screen approximately 100 total subjects, as we assume there will be subjects who may sign the consent form, but ultimately do not participate in the study due to screen failure, not meeting inclusion/exclusion criteria, and personal choice.

Randomization will be provided by the biostatistician from Weill Cornell Medical College. The randomization list will be provided to the principal investigators.

Data Analysis:

For the primary analysis, we will compare the mean change in drug levels of tenofovir diphosphate (TFV-DP) in red blood cells using dried blood spots between week 0 and week 12 in the AdhereTech intervention group compared with the standard of care group via a two-sided t-test. If the data will not meet the normal assumption, non-parametric Wilcoxon Rank Sum test will be used to test medians between two groups.

For the secondary analyses, we will:

- Calculate the mean percentage of patients who complete the 12 week AdhereTech intervention and compare that with the percent that complete 12 weeks of follow-up in the standard of care group.
- Compare the mean change in TFV-DP blood spot level with TFV plasma level and self-reported medication adherence from weeks 0 and 12 between the AdhereTech intervention and standard of care groups.
- Compare the mean change in HIV level and median percent of patients with an HIV RNA below the level of detection from weeks 0 and 12 between the AdhereTech intervention and standard of care group.

These analyses will be performed via two-sided t-tests.

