Initial analysis will be performed based on an intent-to-treat basis. An additional secondary per-protocol analysis will also be performed, including only those patients who completed the intervention originally allocated and excluding patients who discontinued the AdhereTech study intervention early for reasons clearly not related to the intervention (i.e. HIV regimen changed by primary provider, imprisonment, or relocation).

HUMAN SUBJECTS CONCERNS:

Recruitment:

Recruitment will occur via various means. First, physicians and nurse practitioners caring for people with HIV within the Weill Cornell Center for Special Studies and Primary Care clinics will be notified of the study and asked to identify potentially eligible patients who meet the inclusion criteria from a review of their case records. These providers: (1) will ask potential participants: if they are interested in participating in the study, and if so, to call one of the investigators, or the research coordinators, or (2) will identify patients who would be suitable for the study and contact the patients via mail. He/she will mail a letter and a study flyer describing the study to the patients inviting them to call the research team for more information. Samples of the letter and study flyer are provided in Appendices G-J. Patients will be approached only by their clinical care providers and not by any members of the research team. Second, the IRB-approved recruitment fliers will be posted in the Weill Cornell Center for Special Studies and Primary Care clinics. Third, potential participants will be identified via current use of tenofovir and this protocol's inclusion/exclusion criteria by a search of Weill Cornell/NYPH medical records. Potential study participants will be

approached for participation in this study only by their primary medical providers and not by the study investigators. Prior to obtaining informed consent, potential participants will be screened for eligibility according to the inclusion and exclusion criteria specified. Once it is determined that participants meet these criteria and have provided informed consent, additional screening as specified in the Study Time Line will be conducted between weeks -2 and 0.

Consent Process:

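### The secondary per-protocol rule names regimen-change exclusions only for the AdhereTech arm, so a control taken off tenofovir can stay in and tilt the comparison towards the device

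*Combined protocol and SAP*

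**What the plan says.** All references are to the combined protocol and SAP.

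- **Data Analysis, last paragraph.** Intention-to-treat comes first. A further secondary per-protocol analysis keeps patients who finished what they were allocated, "excluding patients who discontinued the AdhereTech study intervention early for reasons clearly not related to the intervention". The examples given are a regimen change by the primary provider, imprisonment and relocation.
- **HIV Therapy.** If the treating provider ends a tenofovir-based regimen, the reason is recorded, "the adherence intervention will be discontinued, and the patient will remain in the study for the purpose of an intention-to-treat analysis". This applies to a patient in either arm.
- **Discontinuing a Patient.** Incarceration and change of residence are among the grounds for discontinuing a patient in either arm when follow-up becomes unlikely. Such patients are also kept for intention-to-treat.
- **Study Overview and Table 1.** Controls receive usual care with routine adherence counseling. Table 1 schedules the counseling at week 0 only.
- **Data Analysis, first secondary analysis.** AdhereTech patients are counted on completing the 12-week intervention, and controls on completing 12 weeks of follow-up. Nothing is said about staying on tenofovir.
- **Background.** TFV-DP is "a compound with a long half-life of 17 days in cells".

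**The concern.** The endpoint is a metabolite of tenofovir itself. When a provider stops the drug, TFV-DP falls whatever the patient's adherence. A per-protocol analysis could set such patients aside, and this one does so explicitly for the AdhereTech arm.

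A control has no bottle to give up. The week-0 counseling has already been delivered, and a control who keeps attending completes follow-up. On that reading a switched control meets the inclusion clause and escapes the exclusion clause. The control mean change is pulled down, the AdhereTech mean is not, and the difference appears as a device benefit. At stake is the one planned analysis that tries to separate adherence from prescribing changes.

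**Working it through.** **Planning figures.** Sample Size Estimate: "we expect to see the same mean concentration (standard deviation) at both groups at baseline: 900 (404) fmol/punch"; at week 12, 1332 (597) against 900 (404), a difference of 432; 32 per arm, "based on a two-sided, two-sample t-test with equal variance". With 597 as the common SD, n per arm = 2 × (1.960 + 0.842)² × 597² / 432² = 30, or 31 with the exact t-test. The stated 32 is reproduced to within two patients, and this point does not affect it.

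**Residual TFV-DP after a stop.** Fraction left after d days = 2^(−d/17).

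| Tenofovir stops at | Days off at week 12 | Fraction left | Loss from 900 |
|---|---|---|---|
| Week 2 | 70 | 0.06 | 848 |
| Week 4 | 56 | 0.10 | 808 |
| Week 6 | 42 | 0.18 | 738 |
| Week 10 | 14 | 0.56 | 391 |

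With stops spread evenly over 84 days, the mean fraction left = 17 / (84 × ln 2) × (1 − 2^(−84/17)) = 0.28. The mean loss is 900 × 0.72 ≈ 646.

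**Bias with no device effect.** Switched AdhereTech patients are removed and switched controls are kept, so bias = (share of controls switched) × (mean loss). The share is not in the documents; 5% and 10% are assumptions.

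| Share switched | Stops spread evenly | All off for last 8 weeks |
|---|---|---|
| 5% | 0.05 × 646 ≈ 32 (7% of 432) | 0.05 × 808 ≈ 40 (9%) |
| 10% | 0.10 × 646 ≈ 65 (15%) | 0.10 × 808 ≈ 81 (19%) |

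By count, with 35 controls and a week-6 stop, one switch gives 738/35 ≈ 21 fmol/punch, two give 42 and three give 63.

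**False-positive rate.** These are simulated change-score t-tests with no true effect and SD 404 at both visits. With 32 per arm and within-patient correlation 0 or 0.5, the two-sided error (nominal 5%) is:

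- stops spread evenly: about 6% at a 5% share and 7 to 9% at a 10% share;
- all off for 8 weeks: about 6% and 8 to 11%;
- exactly one switched control: about 5%; exactly two, with stops spread evenly: under 6%.

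The excess falls on one side. With 35 per arm, a week-6 stop and correlation 0.25 to 0.75, the chance of a significant result favouring AdhereTech (nominal 0.025) is 0.034 to 0.040 for one switched control and 0.064 to 0.091 for three.

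**Same rule in both arms.** With a week-6 stop and correlation 0.5, removing two or five switchers from each arm gives a bias of about 0 and a rate favouring AdhereTech of 0.025. As worded, the same settings give about +42 and 0.051 for two, and +105 and 0.13 for five.

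**The case against.** The best defence is that no sentence puts switched controls in the per-protocol set. The inclusion clause covers both arms, and HIV Therapy keeps switched patients for intention-to-treat, naming no other analysis. A team could fairly read the two together as removing switchers from the per-protocol set in either arm. This stands as a limit on confidence. It does not settle the matter, because completion for controls is measured only by follow-up, and the one explicit exclusion names the AdhereTech intervention.

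A reader might infer that imprisonment and relocation are handled just as unevenly. The documents do not support that. Under Discontinuing a Patient, a control lost for those reasons does not complete follow-up, so the inclusion clause removes most of them, and many would have no week-12 sample. The point concerns regimen changes.

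A reader might also infer that every switched control arrives at week 12 with almost no TFV-DP. That holds only for early stops; a week-10 stop leaves 56%.

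Eligibility requires that no change of regimen be planned and excludes patients with an anticipated treatment interruption, so switches should be few. At 5% of 32 controls the expected number is 1.6.

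Finally, switchers kept in both arms may cost the intention-to-treat analysis some power. That is a separate matter; it does not arise from this asymmetry, and this fix would not change it.

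**Conclusion.** Wrong as written; minor severity, moderate confidence. The exclusion is stated for one arm only, and read with the sections on control care, completion and retention it lets a switched control remain while a switched AdhereTech patient leaves. Any resulting bias favours the device.

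Under the assumed 5 to 10% switch rate it is about 32 to 65 fmol/punch with evenly spread stops, or 40 to 81 with 8 weeks off. This rests on a 17-day half-life, a prior level of 900, a replacement regimen without tenofovir, a week-12 sample from each switched control, and switchers otherwise resembling the rest of their arm. With one or two switched controls the effect is small. It could colour the secondary per-protocol result; it does not touch the primary intention-to-treat comparison.

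**What to change.** Keep intention-to-treat as the initial analysis. Define the per-protocol set by one rule for both arms: exclude any participant, AdhereTech or control, whose provider ended the tenofovir-based regimen, or who was imprisoned or relocated, before week 12. Report the number and timing of these exclusions by arm.

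The cost is a sentence or two in Data Analysis. The reason for a regimen change is already to be recorded, so no new visit or sample is needed; the date should be captured with it. The downside is that a few controls leave a secondary analysis.

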U.S. Department of Health and Human Service, Guidelines for the Use of Antiretroviral Agents in HIV-1-Infected Adults and Adolescents, 2/12/13, available at www.aidsinfo.nih.gov

Watson A. Vitality GlowCaps Trials with Mass General Hospital and Harvard Center for Connected Health. 2008, available at <http://www.connected-health.org/events/past-events/symposium-2008/presentations.aspx>

Protocol Addendum (09-30-2016):

Addendum to Data Analysis Plan:

Due to enrollment being slower than anticipated as of August 2016 (40 of 70 total participants enrolled), we will perform an interim analysis of the tenofovir dried blood spot data for the primary endpoint. The statistician will be blinded to the participants' study group assignments. The statistician will notify us if there is a significant difference detected in the tenofovir dried blood spot levels between the two groups, but the study investigators will be blinded as to the detailed results. Such information will help us determine whether further enrollment into the study is justified. If the difference seen is $</= 5\%$ at the 5% level of significance, study enrollment will be terminated due to futility of the intervention. If the difference seen is $>/= 20\%$ at the 5% level of significance, the study will be terminated due to a significant difference demonstrating efficacy of the Intervention. If the difference is between 6-19%, study enrollment will continue as previously planned until the target sample size of 70 subjects is achieved.

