Hypothesis: The use of a novel adherence intervention (the AdhereTech bottle with reminders) will improve adherence to HIV medications over 12 weeks.

Primary Objective: To assess adherence to a tenofovir-based regimen over 12 weeks in patients using the AdhereTech bottle with reminders compared to the usual standard of care.

Primary Endpoint: The mean change in drug levels of tenofovir diphosphate (TFV-DP) in red blood cells using dried blood spots between week 0 and week 12 in the AdhereTech intervention group compared with the standard of care group.

Secondary Objectives:

- 1) To assess the feasibility of using the AdhereTech bottles with phone/text reminders in HIV-infected patients.
- 2) To assess the use of tenofovir diphosphate dried blood spots as a marker of HIV medication adherence in comparison with plasma tenofovir levels and self-reported medication adherence.

Secondary Endpoints:

- 1) The percentage of patients completing the 12 week AdhereTech intervention in comparison with the standard of care group.
- 2.1) Compare the mean change in TFV-DP blood spot level, TFV plasma level, and self-reported medication adherence between weeks 0 and 12 in the AdhereTech intervention and standard of care groups.
- 2.2) The mean change in HIV level and percent of patients with an HIV RNA below the level of detection between weeks 0 and 12 in the AdhereTech intervention and standard of care group.

RESEARCH PLAN:

Selection of Participants

Type of the Participant Population

This study is open to all adults who meet the following inclusion and exclusion criteria.

Inclusion and Exclusion Criteria:

Inclusion Criteria:

- Male and nonpregnant female subjects aged 18 years and older
- A diagnosis of HIV-1
- Undergoing therapy with a tenofovir-based antiretroviral regimen
- Suboptimal adherence to the tenofovir-containing HIV antiretroviral regimen over the prior 52 weeks from the time of enrollment, as evidenced by 2 HIV RNA levels above the level of

detection following an HIV RNA level below the level of detection, with no plans to change the current HIV drug regimen.

- Access to and willingness to use a cell phone to receive voice/text reminders to take HIV medications. Subjects must also agree to maintain a stable phone number and active cell phone service for the duration of the study.
- Adequate English to provide written, informed consent and to provide reliable responses to the study interview

Exclusion Criteria:

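### The interim futility stop in the 30 September 2016 addendum requires a difference of 5% or less that is also significant, so a flat result cannot trigger it

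*Combined protocol and SAP*

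**What the plan says.** The addendum to the data analysis plan (Protocol Addendum, 09-30-2016) adds one interim look at the primary endpoint because 40 of 70 participants had been enrolled by August 2016. Its purpose is stated as "Such information will help us determine whether further enrollment into the study is justified". Three bands follow:

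- A difference of 5% or less: "at the 5% level of significance, study enrollment will be terminated due to futility of the intervention".
- A difference of 20% or more, with the same significance phrase: "the study will be terminated due to a significant difference demonstrating efficacy of the Intervention".
- In between: "If the difference is between 6-19%, study enrollment will continue as previously planned" to 70. No significance condition is attached.

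The addendum does not say what the percentage is a percentage of, or whether the difference is signed. It also says: "The statistician will be blinded to the participants' study group assignments".

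The primary endpoint is "The mean change in drug levels of tenofovir diphosphate (TFV-DP) in red blood cells using dried blood spots between week 0 and week 12", compared between arms by a two-sided t-test (Data Analysis). The Sample Size Estimate says "we expect to see the same mean concentration (standard deviation) at both groups at baseline: 900 (404) fmol/punch". At week 12 it expects 1332 (SD 597) with the intervention and 900 (SD 404) in control.

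**The concern.** A futility rule is meant to act when the arms look alike. This one asks that they look alike and also differ significantly. An exactly flat result has p = 1 and can never qualify, whatever the sample size.

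The continuation band starts at 6%, so a small non-significant difference falls outside both provisions. The interim was added to inform whether to keep enrolling, and the result that bears most directly on that question has no stated action. Investigators are to hear only whether significance was reached, so they could not tell such a result from one in the continuation band. At stake are up to 30 further enrolments (70 - 40), and whether the decision is fixed in advance or made once the data are known.

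**Working it through.** **Inputs.** From the Sample Size Estimate: baseline 900 (SD 404) in both arms; week 12 at 1332 (SD 597) against 900 (SD 404), a difference of 432; two-sided 5% level. From the addendum: 40 enrolled. Assumed: 20 per arm (1:1 allocation), all with week-12 samples; percentages taken of 900, so 5% is 45 fmol/punch; week 0 to week 12 correlation rho from 0 to 0.9, because the protocol gives none.

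**The plan's own figure.** n per arm = 2 × (1.960 + 0.842)² × SD² / 432². With SD 597 in both arms this gives 30 (31 with the t-distribution), close to the stated 32; t-test power at 32 is 0.813. The root-mean-square SD of 509.7 gives only 22 to 23. The plan's 32 therefore corresponds to the larger SD in both arms.

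**Smallest significant difference at the interim** = t(0.975, 38) × SD × √(2/20), with t = 2.0244.

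- Week-12 levels, SD 404: 2.0244 × 404 × 0.3162 = 258.6, or 28.7% of 900. SD 597: 382.2, or 42.5%.
- Change scores, SD = 404 × √(2(1 - rho)):

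| rho | SD of change | Smallest significant difference | % of 900 |
|---|---|---|---|
| 0 | 571.3 | 365.8 | 40.6 |
| 0.5 | 404.0 | 258.6 | 28.7 |
| 0.8 | 255.5 | 163.6 | 18.2 |
| 0.9 | 180.7 | 115.7 | 12.9 |

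For 45 fmol/punch to be significant, the SD would have to be 45 / (2.0244 × 0.3162) = 70.3. On change scores that means rho = 1 - (70.3/404)²/2 = 0.985.

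**How often each outcome occurs with no true effect** (simulated, pooled t-test, 20 per arm):

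- Unsigned difference of 5% or less and significant: 0.0% in every scenario.
- Signed difference of 5% or less and significant: 2.5%, all favouring control.
- Unsigned difference of 5% or less and not significant: 28% (SD 404) and 19% (SD 597) on levels. By hand, P(|Z| ≤ 45/(404 × 0.3162)) = P(|Z| ≤ 0.352) = 0.275. On change scores: 20%, 28%, 42% and 57% at rho 0, 0.5, 0.8 and 0.9.
- Signed difference of 5% or less and not significant: 61% on levels (SD 404); 57% to 69% on change scores (rho 0 to 0.8).

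**Under the planned 432 effect, on levels.** A significant difference of 20% or more occurs in 74% of interims with SDs 597/404, and in 61% with SD 597 in both arms. A non-significant difference of 20% or more, also without a stated action, occurs in 20% and 30%.

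**The case against.** The best defence is that the significance phrase names only the level at which the comparison is tested. The three bands then cover every rounded result, as they were probably meant to, and a flat result does stop enrolment. This is a possible reading, but the efficacy sentence uses the same phrase and glosses it as a significant difference. If the phrase imposes no condition, the efficacy stop rests on that gloss alone. If the gloss too is treated as description, a signed difference of 20% or more would occur in 8% to 17% of null interims on levels (SD 404 to 597). The two readings lead to different actions on the same data, so the text has to choose.

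A reader might go further than the documents allow in four ways:

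- **That the trial is left with no course of action.** Study Design and the Sample Size Estimate both plan for 70, so continuing is a plausible default when no stop is met. The failure is a futility stop that does not fire, plus an action left to judgement.
- **That the efficacy stop fails too.** As written it can fire, as the 61% to 74% above shows.
- **That the percentage is undefined.** A percentage of the expected control change (900 to 900, so zero) would be. But the addendum speaks of levels, and a percentage of the comparator's level is the natural reading. The missing base and sign are a minor omission.
- **That the futility wording inflates type I error.** It does not. Testing at 5% at both looks does, which is a separate matter.

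The defence can also say that the stated study risk, blood drawing, is described as minimal, so over-enrolment does limited harm. That bears on urgency, not on whether the rule works.

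**Conclusion.** The futility stop is wrong as written. On the literal text, a flat or near-flat interim cannot trigger it: 0.0% of null interims unsigned, and 2.5% signed, all favouring control. A non-significant difference of 5% or less, 19% to 28% of null interims on levels, falls between the stop and the continuation band.

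The size rests on 20 per arm with complete data, a base of 900, the protocol's SDs and an assumed rho. The conclusion does not depend on them within the ranges shown. With fewer week-12 samples the gap widens: at 16 per arm, significance on levels needs 32% to 48% of 900. The looser reading of the phrase does not remove the need for a rewrite, because it conflicts with how the efficacy sentence explains itself.

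**What to change.** Replace the three bands with exhaustive outcomes on the signed difference (AdhereTech minus control) in the week 0 to week 12 change in TFV-DP:

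- (a) Stop for efficacy only if a pre-stated significance boundary is crossed in favour of AdhereTech.
- (b) Stop for futility if the estimate is at or below a stated value, with its base given and no significance condition. The sponsor's statistician sets the value and reports its chance of stopping under the planned 432 fmol/punch effect.
- (c) Otherwise continue to 70.

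As an illustration only, a cut-off of 45 fmol/punch would stop 60% to 71% of null interims on change scores (rho 0 to 0.8). Under the 432 effect it would stop 3.0% at rho 0 and 0.5% at rho 0.5. If the true benefit were 180 (20% of 900), it would stop 14% on levels with SD 404 in both arms, or about 20% with SDs 597/404.

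The cost is one paragraph, with no extra participants or samples. Because the statistician is blinded to assignment, the text must say who decodes the direction; that person learns which arm is ahead.

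A related but separate choice is the efficacy boundary. Testing at 5% at 40 and again at 70 gives an overall two-sided level of about 8.1%. An O'Brien-Fleming-type split (0.006 interim, 0.048 final) keeps 5%. Under the 432 effect, with 35 per arm and no dropout, its price is:

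| Assumption | Early efficacy stop, 5% at both looks | Early efficacy stop, split | Overall power, either way |
|---|---|---|---|
| Levels, SDs 597/404 | 74% | about 42% | about 94% |
| Levels, SD 597 in both arms | 61% | about 28% | about 85-86% |
| Change scores, rho 0 | 53% | about 23% | about 78-81% |

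Overall power falls by about 1 to 3 points.
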